3. EFFICACY AND SAFETY ASSESSMENT

	Screening period	Pre-treatment period						Tre	atmen	t Perio	d			Follow-up period
	Up to 3 weeks before							Week	(2		Week 3			Week 4 to 5
	pre-treatment period	treatment period	D1	D2 &D3	D4	D5	D8	D9 & D10	D11	D12	D15	D16&D17&D18	Final visit D19 /ET	D26 +/- 2
Informed Consent Form	Х													
Demographics and Medical history	Х													
Previous treatments and procedures	Х													
Physical examination	Х												Х	
Vital signs	Х		Х										Х	
ECG	>	ζb											Х	
Ophthalmic examination	>	(b											Х	
Inclusion Criteria and Exclusion Criteria	Х		Х											
Selection of target sites	Х		Х											
Urinalysis	Х												Х	
Safety tests Blood sampling	Х												Х	
Randomization			Х											
Local Tolerance °				D2 only	Х		Х		Х		Х		Х	
Individual clinical scores	Х		Х		Х		Х		Х		Х		Х	
Clearing score					Х		Х		Х		Х		Х	
Keratolytic product application of selected plaque at home daily		Х												
Products application			Х	Х	Х	Х	Х	Х	Х	Х	Х	Х		
CCI														
PK blood sampling						Х							Х	Х
CCI														
Concomitant treatments and Procedures	Х	Х	Х	Х	Х	Х	Х	Х	Х	Х	Х	Х	Х	Х
Adverse events d	Х	Х	Х	Х	Х	Х	Х	Х	Х	Х	Х	Х	Х	Х
Exit form ^e													X f	Х

a. if the scaling score did not reach 0 or 1 after 1 week of pre-treatment, the pre-treatment period can be extended to 2 weeks, otherwise the subjects will start D1 visit immediately. b ECG and ophthalmic exams should be done as close as possible to baseline visit. c Local tolerance CCI weeks of the concerned zone must be taken at any visit in case of AE in a treatment zone. d Adverse Events have to be collected from the ICF signature. e Exit form should be signed after subject data collection has been completed. f Exit form should be completed at ET visit only if no follow-up visit is planned (discontinuation)

4. EFFICACY AND SAFETY VARIABLES

4.1. Efficacy variables

Primary clinically efficacy criteria

Area Under the Curve (AUC) from Day 1 to Day 19 of Total Sum Score (TSS) (sum of erythema, scaling and induration scores).

Secondary clinically efficacy criteria

- AUC of individual clinical scores (erythema, scaling and induration) from Day 1 to Day 19.

Erythema is scored on the following 5-point scale:

0	None	No detectable erythema.
1	Mild	Slight pinkness present
2	Moderate	Definite redness, easily recognized.
3	Severe	Intense redness
4	Very Severe	Very intense redness

Scaling is scored on the following 5-point scale:

0	None	No shedding
1	Mild	Barely perceptible shedding, noticeable only on light scratching or rubbing.
2	Moderate	Obvious but not profuse shedding
3	Severe	Heavy scale production
4	Very Severe	Very thick scales

Induration is scored on the following 5-point scale:

0	None	Normal skin thickness. No elevation of skin		
1	Mild	Barely perceptible elevation (by touching) of the psoriasis plaques.		
2	Moderate	Obvious elevation above the normal skin level; moderate thickening		
3	Severe	Definite thick elevation above normal skin level		
4	Very Severe	Very thick elevation		

- TSS at each visit (screening, end of pre-treatment period for Z1 and Z2, day 1, day 4, day 8, day 11, day 15 and day 19) and TSS percent change from baseline;

- Erythema, scaling and induration score at each visit: screening, end of pretreatment period for Z1 and Z2, day 1, day 4, day 8, day 11, day 15 and day 19) and their change from day 1;

- Success rate (defined as a clearing score of 0 or 1) at each evaluation visit (day 4, day 8, day 11, day 15 and day 19) and the time to first success.

Protocol No: RD.03.SPR.112075 Statistical Analysis Plan Page 10 of 38

The clearing score is defined as:

0	Complete clearing	No scaling and no infiltration even on palpation. Post inflammatory hypo- or hyperpigmentation may be present.
1	Almost clear	Residual erythema with some induration/ infiltration (not clinically visible but palpable) without scaling, or residual erythema and residual scaling with no infiltration.
2	Unchanged	Unchanged or less than almost clear.

The time to partial clearing (clearing score of 0 or 1) is defined as:

0	No Success at any day
1	Success at Day 19 and not before
2	Success at Day 15 and not before
3	Success at Day 11 and not before
4	Success at Day 8 and not before
5	Success at Day 4 and not before

Only the earliest day of success will be considered in defining the time to partial clearing, independently of the subsequent days.

CCI		

4.2. Safety variables

- Local tolerance (irritation, stinging/burning, pruritus) twice weekly using a 4-point scale for each mini-zone:

Irritation	Skin irritati	Skin irritation Assessment						
0	None:	No signs of irritation						
1	Mild:	Slight signs of irritation						
2	Moderate:	Adderate signs of irritation: Obvious increase in redness as compared to the on-treated surrounding area						
3	Severe:	Severe signs of irritation						
Stinging/ Burning	Prickling pa	ling pain sensation						
0	None:	No stinging/burning						
1	Mild:	Slight warm, tingling/stinging sensation; not really bothersome						
2	Moderate:	Definite warm, tingling/stinging sensation that is somewhat bothersome						
3	Severe:	Hot, tingling/stinging sensation that causes severe discomfort						
Pruritus	Itch sensatio)n						
0	None:	No itching						
1	Mild:	Itching is noticeable but not really bothersome						

2	Moderate:	Definite itching that is somewhat bothersome
3	Severe:	Marked itching, urge to scratch and causes definite discomfort

- Incidence and multiplicity of Adverse Events (from informed consent signature to the end of the study);
- Ophtalmic examination at screening and day 19/ET
- Physical examination at screening and day 19/ET;
- Vital signs performed after 5 minutes rest in the sitting position (systolic blood pressure, diastolic blood pressure, pulse rate, vital signs evaluation) at screening, baseline and day 19/ET;
- 12-lead electrocardiogram during the screening period and at day 19/ET;
- Blood samplings for laboratory safety tests (haematology and blood chemistry) at screening and day 19/ET (Virology will be performed only at screening);
- Urinalysis at screening and day 19/ET;

CC

5. **POPULATIONS ANALYZED**

5.1. The Intent-to-treat (ITT) population

The ITT Population is defined as comprising all subjects who are randomized.

Protocol No: RD.03.SPR.112075 Statistical Analysis Plan Page 12 of 38

5.2. The Per-Protocol (PP) efficacy population

This population will consist of ITT subjects, except some subjects considered as not evaluable due to major deviations from protocol.

Major deviations will be defined after data entry and before breaking the treatment blind, and may include: inclusion criteria not respected, interfering therapy, protocol deviation, poor compliance to study treatment administration or protocol requirements, unblinding. The decision on determining whether a subject is excluded from the per-protocol (PP) population will be made during the blind review meeting.

If no patient has a major deviation, PP efficacy population will be the same as ITT population, and results will be presented on the ITT population only.

5.3. The Safety population

Safety population corresponds to all subjects who received at least once the study treatment during the treatment period.

In case of identical populations, only one safety population will be used for the analysis.

7. STATISTICAL METHODS AND DATA CONSIDERATIONS

SAS[®] version 9.3 will be used for the analysis. Graphics will be performed on SAS.

The categorical variables will be summarized by frequency and percentage for each response category (N, %). The continuous variables will be summarized using means, medians, minimum, maximum, and standard deviations.

7.1. Study subjects

7.1.1. Disposition of subjects

Subject disposition will be summarized in the ITT population.

Normal completion as well as early discontinuation will be summarized using frequency distribution (n, %). All early discontinuations will be detailed in a subject-by-subject listing.

7.1.2. Protocol deviations

All protocol deviations, including the decisions regarding major/minor protocol deviations, will be documented in the blind data review meeting and entered into a dataset.

Subjects with major protocol deviations will be excluded from the PP population.

Major protocol deviations will be summarized using frequency distribution (n, %) and will be detailed in a subject-by-subject listing.

7.2. Efficacy analysis

7.2.1. Data sets analyzed

Number of subjects included in each population (ITT population, PP population, safety population, ^{CCI}) will be summarized.

7.2.2. Demographic characteristics

Frequency distribution (n, %), for qualitative criteria, will be used.

Usual descriptive statistics (n, mean, standard deviation, median, min, max), for quantitative criteria, will be used.

Analysis will be performed on ITT population and PP population (if the number of patients is too different).

7.2.3. Medical history, previous and concomitant therapies, medical and surgical procedures

Medical history will be defined as any disease present before the Screening visit.

Frequency distribution of subjects with previous or/and concomitant disease(s) will be tabulated. Previous and concomitant therapies will be coded using the World Health Organization (WHO) Drug Dictionary (version v032015).

Previous therapies are defined as therapies stopped within the 6 months preceding the screening visit. Frequency distribution of subjects with at least one previous therapy will be tabulated by Anatomical Therapeutic Chemical (ATC) classification.

Concomitant therapies are defined as any ongoing therapies at the time of the screening visit, and any new therapies started or changed since the screening visit.

Frequency distribution of subjects with at least one concomitant therapy will be tabulated by ATC classification.

Previous and concomitant procedures will be coded using the Medical Dictionary for Regulatory Activities (MedDRA version 18.0).

Previous procedures are defined as procedures stopped within 6 months preceding the screening visit.

Protocol No: RD.03.SPR.112075 Statistical Analysis Plan Page 15 of 38

Frequency distribution of subjects with at least one previous procedure will be tabulated (n, %) by preferred term.

Concomitant procedures are defined as any ongoing procedures at the time of the screening visit, and any new procedures started or changed since the screening visit.

Frequency distribution of subjects with at least one concomitant procedure will be tabulated (n, %) by preferred term.

7.2.4. Compliance

extreme cream will be applied at home by the subject twice daily, up to 2 weeks before the treatment period upon the judgment of the dermatologist. The scaling score should be 0 or 1 when the subject is enrolled.

All applications during the treatment period will be performed by a person from the investigational team at the study centre, once daily during 3 weeks, 5 days a week except for the third week, for a total of 14 applications.

Subjects with a low compliance will be excluded from PP population during the data review.

7.2.5. Efficacy analysis

7.2.5.1 Primary and secondary efficacy analysis

Descriptive statistics will be done on observed cases for PP and ITT populations.

The Area Under the Curve (AUC) will be calculated from Day 1 (before application) to Day 19 by subject and by treatment/pre-treatment on the Z1-Z6 mini-zone, using the trapezoidal rule on ITT and PP population.

Dates of theorical visit will be used to perform AUC.

AUC of TSS will be submitted to an analysis of variance including subject and treatment/pretreatment as factors in the model, ^{CCI}

AUC of individual clinical scores (erythema, scaling and induration) will be submitted to the same variance analysis.

TSS and TSS percent change from day 1 will be descriptively summarized by visit, as the individual score of erythema, scaling and induration and their respective change from day 1. The analysis will be performed on PP population and ITT population (baseline and Endpoint/LOCF) Success will be presented in frequency tables (N,%) by treatment/pre-treatment and by visit. The time to first success will be summarized by treatment/pre-treatment.

7.2.6. Statistical and analytical issues

7.2.6.1 Adjustment for covariates

Adjustments to baseline value, i.e., day 1 will be considered in the calculation of change and percent change.

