5.3 Inclusion criteria

- 1. Adult male or female aged at least 18 and up to 70 years old inclusive at screening visit.
- 2. Female of non-childbearing potential (postmenopausal [absence of menstrual bleeding for 1 year prior to screening, without any other medical reason], hysterectomy or bilateral oophorectomy).
- 3. Subject has a skin phototype I to IV on Fitzpatrick's scale. (Screening visit).
- 4. The subject has a clinical diagnosis of stable plaque psoriasis, defined as no flare during the month before Screening visit and no change between Screening visit and Baseline visit, of mild to moderate severity. (Screening visit and Baseline Visit).
- 5. The subject presents with at least six eligible mini-zones, on at least two psoriasis plaques (Screening visit and verified also at Baseline Visit) which:

Protocol No.: RD.03.SPR.112075 V01 16 Aug 2016

Page 33 of 85

- 5.1. are located on the upper and/or lower extremities (anterior crest of tibia, apex of knees and apex of elbows excluded) and/or on the trunk. Plaques on the face, scalp, hands, feet and folds will not be eligible as test areas.
- 5.2. have a Total Sum Score (TSS = erythema + induration + scaling) \geq 6 before desquamation; each item separately being \geq 2,
- 5.3. have identical severity (i.e. identical TSS or variation of ± 1 grade) before desquamation,
- 5.4. are approximately 2 cm in diameter and at least 2 cm apart from each other.
- 5.5. for the two desquamated zones at Baseline visit:
 - 5.5.a. have a scaling score of 0 or 1,
 - 5.5.b. have identical severity between the zones or variation of ± 1 grade for the sum of induration and erythema scores, each item separately being ≥ 2
- 6. Subject agrees not to wear his/her contact lenses from the Baseline visit till the D19 visit, (Screening visit)
- 7. Subject is willing and able to comply with all of the time commitments and procedural requirements of the clinical trial protocol. (Screening visit)
- 8. Subject understands and signs an Informed Consent Form (ICF) at screening, prior to any investigational procedures being performed. (Screening visit)
- 9. The subject is covered by a National Social Security System (Screening visit)

Rationale:

Criterion	Rationale
1	To ensure appropriate age requirements for adults
2	No reproduction toxicity studies conducted with this IMP to date.
3	To allow proper assessment of clinical and biophysical skin imaging evaluation

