8.1.2 Baseline visit [Day 1]

At the Baseline visit, the Investigator or designee will:

- 1. Ask the subject about AEs using an open-ended question, such as "Have you noticed any change in your health since the last visit?" Record all events, as appropriate, on the corresponding CRF form(s).
- 2. Check laboratory results hematology, biochemistry, virology, urinalysis from the Screening visit.
- 3. Ask the subject about any changes in his/her concomitant therapies/procedures (added, removed or changed) since the previous visit. Record all changes in the source document and the CRF.
- 4. Check vital signs
- 5. Confirm the six target mini-zones according to the inclusion criteria,

For non-desquamated zones TSS (erythema + induration + scaling) should be superior or equal to 6 on a 13 point scale (0 to 12), with individual score of erythema, induration and scaling separately being ≥ 2 . The zones must present a similar severity, i.e.: identical Baseline TSS or variation of ± 1 grade.

For desquamated zones scaling score should be equal to 0 or 1 on a 5 point scale (0 to 4), and individual score of erythema, and induration separately being ≥ 2 . The zones must present a similar severity, i.e.: identical Baseline sum of erythema and induration or variation of ± 1 grade.

- 8. Confirm subject meets inclusion/exclusion criteria.
- 9. Assign a randomization number to the Subject (this number will be assigned to randomized Subjects in increasing order and no numbers will be omitted).

10.

A member of staff other than the Investigator will:

- 11. Apply 50µl of the tested products on the Subject's selected mini-zones according to the randomization list generated by the sponsor and in compliance with the operational manual.
- 12. Instruct the Subject to avoid wetting areas (swimming, bath, sauna, hammam are not allowed). However, showers are permitted at least eight hours following applications.
- 13. Complete the Subject Enrollment Log and subject identification code list.
- 14. Schedule the next visits (D2 to D19).

nternally Approved 01-Feb-2019

CONFIDENTIAL GALDERMA

Protocol No.: RD.03.SPR.112075 V01 16 Aug 2016

Page 70 of 85

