8.2 Subject instructions (other than study drug(s) administration)

Each subject will receive specific requirements or instructions to follow until the end of the study.

During the study, the Subject will be allowed to use, if needed, all types of therapies excluding those listed in the 5.5.5 Prohibited concomitant therapies.

Subjects will be instructed not to apply any treatment oremollient to the target psoriasis plaques receiving the pre-treatment or the treatments during the study. Subjects may treat the other psoriasis plaques (other than the one(s) with selected mini-zones) only with their regular emollient, or using the emollient provided by the Sponsor.

Scalp psoriasis may be treated with non-steroid shampoo.

The Subject will be instructed to apply the keratolytic product at home every day two times per day, preferably after washing, from 7 days before the planned Baseline visit appointment on the plaque(s) selected by the investigator only and not on the other plaques. No application should be performed the day of Baseline visit. This period may be extended to one more week based on investigator judgment.

If a Subject needs to take a concomitant treatment (topical or systemic), he/she should inform the Investigator of it as quickly as possible (at the latest, at the next visit).

The Subject will be instructed to keep the treated areas as dry as possible. Showers will be allowed at least eight hours after the applications. Some additional gauze may be used to protect the treated areas from getting wet (*i.e.* use of "Cellofrais"). Bathing (swimming, bath, sauna, hammam) will be prohibited during the duration of the study. In addition, the Subject will be instructed to avoid excessive sun exposure and vigorous exercise that may result in excessive sweating during the study.

The subjects should never remove the bandages on treated zones.

Protocol No.: RD.03.SPR.112075 V01 16 Aug 2016

Page 73 of 85

The contact lens wearing is prohibited during the treatment period.

The Subject should come to the site each day for study procedures and study drugs applications except on Saturdays and Sundays.

The Subject will be instructed not to discuss the study materials with the Investigator or other Evaluator(s).

For safety precautions, participation in any other clinical trial is prohibited during the course of the study and for the following month.

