9.2. Efficacy analyses

9.2.1. Subjects characteristics

Table. Data sets analyzed

Table. Demographic data – ITT population Including age (as quantitative data and by class 18-64, 65-84 and >=85), gender, race, phototype, subject of childbearing potential.

Table. Medical history – ITT population

Including duration of psoriasis and relevant or major illnesses present before the screening visit.

Table. Previous therapies by ATC term – ITT population

Table. Previous procedures by preferred term – ITT population

Table. Concomitant therapies by ATC term – ITT population

Table. Concomitant procedures by preferred term – ITT population

Statistical Analysis Plan Page 21 of 38 9.2.2. Baseline characteristics

Table. Target location – ITT population

	CD10367 placebo pre-treated	CD10367 3% pre-treated	CD10367 placebo	CD10367 1%	CD10367 3%	Betneval 0.1%	Overall
N							
Elbows	n(%)						
Knees	n(%)						

Table. Target location – PP population

Table. Pre-treatment clinical scores in mini-zones Z1 and Z2 – ITT population

		CD10367 placebo pre-treated	CD10367 3% pre-treated	Overall
Erythema	Ν			
	2			
	3			
	4			
	Mean			
	SD			
	Median			
	(Min,Max)			
Scaling	N			
-	0			
	1			
	Mean			
	SD			
	Median			
	(Min,Max)			
Induration				
TSS				

Table. Pre-treatment clinical scores in mini-zones Z1 and Z2 – PP population

Table. Baseline clinical scores in mini-zones Z1 to Z6 – ITT population

Internally Approved 01-Feb-2019 Protocol No: RD.03.SPR.112075 Statistical Analysis Plan Page 22 of 38

CONFIDENTIAL GALDERMA

Page 22 of 38 Baseline corresponds to week 1 day 1.

Table. Baseline clinical scores in mini-zones Z1 to Z6 – PP population

Baseline corresponds to week 1 day 1.

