9.2.3. Primary and secondary efficacy criteria

Table. AUC of TSS – Treatment period - PP and ITT population

		CD10367 placebo pre-treated	CD10367 3% pre-treated	CD10367 placebo	CD10367 1%	CD10367 3%	Betneval 0.1%
AUC of TSS (PP)	Ν		_				
	Mean						
	SD						
	Median						
	(Min,Max)						
AUC of TSS (ITT)	N						
	Mean						
	SD						
	Median						
	(Min,Max)						

Table. Analysis of variance for AUC of TSS – Treatment period - PP population

		LSmean(SE)	p-value*
Model Effects	Patient	-	
Treatment	CD10367 placebo pre-treated		
Treatment	CD10367 3% pre-treated		
Contrast	 CD10367 placebo – Betneval		
CCI			

Internally Approved 01-Feb-2019 Protocol No: RD.03.SPR.112075

Statistical Analysis Plan Page 23 of 38

Table. AUC of erythema – Treatment period - PP and ITT population

Table. Analysis of variance for AUC of erythema – Treatment period - PP population

Table. AUC of scaling – Treatment period - PP and ITT population

Table. Analysis of variance for AUC of scaling – Treatment period - PP population

Table. AUC of induration – Treatment period - PP and ITT population

Table. Analysis of variance for AUC of induration – Treatment period - PP population

Table. TSS and TSS percent change from day 1 – PP population

TSS		CD10367 placebo pre-treated	CD10367 3% pre-treated	CD10367 placebo	CD10367 1%	CD10367 3%	Betneval 0.1%
Screening	N						
	Mean SD						
	Median						
	(Min,Max)						
End of pre-treatment period*							
Day 1, Day 4	Ν						
	Mean						
	SD						
	Median						
Percent change from Day 1 at Day 4	(Min,Max) N						
reicent change nom Day 1 at Day 4	Mean						
	SD						
	Median						
	(Min,Max)						
Day 8, Day 11, Day 15, Day 19	N						
Percent change from Day 1 at Day	Ν						
8, Day 11, Day 15, Day 19							
	•••						

*performed only in Z1 and Z2

Internally Approved 01-Feb-2019 Protocol No: RD.03.SPR.112075

CONFIDENTIAL GALDERMA

Statistical Analysis Plan

Page 24 of 38 Table. TSS and TSS percent change from day 1 – ITT population

ITT population and with only 2 visits: Day 1 and Endpoint/LOCF

Table. Erythema and change from day 1 – PP population

 Table. Erythema and change from day 1 – ITT population

 Table. Scaling and change from day 1 – PP population

Table. Scaling and change from day 1 –ITT population

 Table. Induration and change from day 1 – PP population

Table. Induration and change from day 1 - ITT population

Table. Clearing score by visit – Treatment period - PP population

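### The visible primary ANOVA of raw AUC of TSS has no zone-level Day 1 term, so precision is lost if the permitted Day 1 gaps between zones persist

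*SAP*

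**What the plan says.** The section headed Adjustment for covariates (SAP 7.2.6.1) is not redacted and reads in full: "Adjustments to baseline value, i.e., day 1 will be considered in the calculation of change and percent change". SAP 7.2.5.1 summarizes change and percent change descriptively only. For the tested endpoint it says "AUC of TSS will be submitted to an analysis of variance including subject and treatment/pretreatment as factors in the model", and the sentence then continues into a redaction. The table shell titled "Analysis of variance for AUC of TSS" (SAP 9.2.3) shows rows for patient, treatment and contrasts and none for Day 1; a redacted block follows it.

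The protocol sets how closely the zones of one subject must match:

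- At selection, all six zones must "have identical severity (i.e. identical TSS or variation of ± 1 grade) before desquamation" (Protocol 5.3).
- At Day 1, the four standard zones must again agree on TSS to within ±1 grade (Protocol 6.1.5.1 and 8.1.2).
- At Day 1, the two desquamated zones must "have a scaling score of 0 or 1", and their matching rule is "identical Baseline sum of erythema and induration or variation of" ±1 grade. Scaling is outside that rule.

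SAP 9.2.2 tabulates "Baseline clinical scores in mini-zones Z1 to Z6" by treatment, so an imbalance would be seen.

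**The concern.** The subject factor takes out each subject's average level. The contrasts of interest compare zones within a subject, and Day 1 differences between those zones stay in the error term. The AUC is raw and includes Day 1, so a zone that starts higher carries that excess into its AUC for as long as it lasts.

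For the desquamated pair the exposure is wider than the matching rule suggests. Erythema plus induration may differ by 1, and scaling may be 0 in one zone and 1 in the other. Day 1 TSS may therefore differ by 2, although the pair was matched on full TSS before desquamation.

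At stake is the precision of the comparisons of CD10367 with its vehicle in each skin condition, with 24 subjects. A chance imbalance would appear in the baseline table, the visible primary test would not adjust for it, and any adjustment chosen at that point would be post hoc.

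**Working it through.** The plan has no figure of its own to reproduce here, because the effect, SD, alpha and power behind the 24 subjects are redacted. Everything beyond the AUC weights and the degrees of freedom is illustrative.

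**Inputs from the documents.** Scoring days 1, 4, 8, 11, 15 and 19, with AUC by the trapezoidal rule on nominal visit days (SAP 7.2.5.1). Day 1 is scored before application (Protocol 7.1.1.1). 24 subjects with six zones each.

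**Assumed.** Residual SD s = 15, true difference 15 TSS-days, two-sided 5%. Standard zones are split evenly over two adjacent TSS grades, so the within-subject Day 1 variance is V = 0.25, the largest possible for two values; an 80/20 split gives V = 0.16. Persistence p is the share of a Day 1 gap that remains at every later visit.

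**Step 1, AUC per grade of Day 1 gap.** The intervals 3, 4, 3, 4, 4 give weights 1.5, 3.5, 3.5, 3.5, 4, 2, which sum to 18. The slope is b = 1.5 + 16.5p: 1.5 (p = 0), 9.75 (p = 0.5), 18 (p = 1). A two-grade gap adds 3 to 36. Fully persistent, one grade is 18/108 = 17% of the AUC of a zone flat at TSS 6 (6 × 18 = 108).

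**Step 2, share of within-subject variance explained by Day 1 TSS:** Vb²/(Vb² + s²).

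- V = 0.25, s = 15: 0.56/225.56 = 0.2%; 23.8/248.8 = 10%; 81/306 = 26%.
- Over s = 10 to 20 the range is 0.1% to 45%.
- V = 0.16, s = 15: 0.2%, 6%, 19%.
- Desquamated pair, b = 13.5 (p = 12/16.5 = 0.73): if the scaling gap fades, (0.25 × 13.5² + 0.25 × 1.5²) = 46.1 and 46.1/271.1 = 17%; if it persists as the other items do, 91.1/316.1 = 29%.

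**Step 3, degrees of freedom.** 144 − 1 − 23 − 5 = 115, or 114 with one covariate.

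**Step 4, simulated power of the vehicle contrast** (subject and treatment fixed, with and without one Day 1 covariate centred within pre-treatment condition; 3,000 runs per scenario, Monte Carlo SE about 0.5 to 0.7 points):

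| Zones | Persistence | Raw | Adjusted |
|---|---|---|---|
| Standard, even split | none | 93% | 93% |
| Standard, even split | half | 90% | 93% |
| Standard, even split | full | 81% | 92% |
| Standard, 80/20 | full | 85% | 92% |
| Desquamated pair | none | 93% | 92% |
| Desquamated pair | erythema and induration persist, scaling fades | 84% | 91% |
| Desquamated pair | full | 79% | 93% |

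A repeat simulation gave 93% v 93%, 91% v 93% and 81% v 92% for standard zones with none, half and full persistence, and 78% v 92% for the desquamated pair with full persistence.

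**Step 5, closed-form check, full persistence, standard zones.** The SE is √(2 × 306/24) = 5.05 raw, against √(2 × 225/24) = 4.33 without the gap. Power is 84% v 93%. To match the precision of 24 subjects without the gap, the raw analysis needs 24 × 306/225 = 33. The simulated 81% is lower because the pooled error also carries the wider gaps of the desquamated pair: the mean added variance is (4 × 81 + 2 × 162)/6 = 108, so the model SE is √(2 × 333/24) = 5.27, and power is about 82%.

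**Step 6, other residual SDs** (V = 0.25, full persistence; adjusted SE = √(2s²(1 + 1/113)/24)):

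| s | SE raw | SE adjusted | Excess | Raw power when adjusted power is 80% |
|---|---|---|---|---|
| 9 | 3.67 | 2.61 | 41% | 51% |
| 18 | 5.81 | 5.22 | 11% | 71% |
| 27 | 8.22 | 7.83 | 5% | 76% |
| 36 | 10.71 | 10.44 | 3% | 78% |

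At half persistence the excess is 13%, 3%, 1% and 0%. If ±1 is read as around a reference value (−1, 0, +1 equally likely, V = 0.67), it is 91%, 29%, 13% and 8% at full persistence.

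**The case against.** **Redaction.** The model sentence is cut exactly where a further term could stand, and redacted text is not missing text. This stands as a limit. Against a hidden term, the covariate section is unredacted and names nothing for the AUC, and the visible shell rows include no Day 1 term.

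**Design.** Zones are matched to within a grade and rechecked on Day 1, products are randomized to zones, subject is blocked, and percent change is reported. Matching with blocking is a legitimate choice in an exploratory Phase 2a study. This stands too: nothing in the plan contradicts itself and there is no systematic bias. It caps the loss but does not remove it, least of all for the desquamated pair, whose Day 1 scaling is not matched.

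**Size.** SD, true difference, gap distribution and persistence are all assumed, and only strong persistence makes the loss large. At quarter persistence a simulation gives about 91% v 92%. The 81% for standard zones partly reflects the pooled error; without the extra scaling variance it is about 83% to 85%, against 93% to 94% adjusted. If a working product shrinks the gap on its own zone (full persistence on vehicle, half on actives), the figures are about 87% v 93%, and a single slope is then only approximate. On the desquamated zones "No application should be performed the day of Baseline visit", so a scaling gap may fade once the keratolytic stops. Finally, if the redacted planning SD came from observed raw AUCs, planned power may already allow for such gaps, so no shortfall against planned power can be shown.

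These points reduce the size. They do not put a Day 1 term into the visible model, and they do not make adding one costly.

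**Conclusion.** The concern holds on the visible text. The primary test uses raw AUC with no zone-level Day 1 term, while the protocol permits within-subject Day 1 gaps of 1 TSS grade (standard zones) and up to 2 (desquamated pair) that the subject factor cannot absorb. The consequence is lost precision and unadjusted chance imbalance, not bias.

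Under the stated assumptions the loss in power runs from nothing when gaps vanish, through about 3 points at half persistence on standard zones, to about 8 to 11 points on standard zones and 14 on the desquamated pair at full persistence. It shrinks as the residual SD grows. The change is recommended rather than essential. Confidence is medium, because the end of the model sentence and the planning SD are both redacted.

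**What to change.** Amend SAP 7.2.6.1 and 7.2.5.1 so that the AUC of TSS model includes the mini-zone's Day 1 TSS as a covariate, and each item AUC model includes the matching Day 1 item score. Centre the covariate within pre-treatment condition. Day 1 scaling differs by design between desquamated zones (0 or 1) and standard zones (at least 2), and an uncentred common slope would adjust away the keratolytic's effect: in a simulation with SD 18 and full persistence it moved a contrast across skin conditions from −36.2 to −0.8 TSS-days. Keep the unadjusted ANOVA as a sensitivity analysis. If the redacted text already contains such a term, 7.2.6.1 should say so.

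Do not subtract 18 × Day 1 TSS from the AUC instead. If the gap fades, simulated power falls from 93% to 84% on standard zones and from 93% to 80% on the desquamated pair.

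The cost is a sentence in the SAP and one model term: 1 of 115 residual df with a common slope, 2 with a slope per skin condition. The Day 1 scores are already collected on every zone before application. If no gap persists, the loss of power is under 1 percentage point.
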